6.2.4 Q-LES-Q-SF

The Q-LES-Q-SF is a patient self-reported questionnaire that assesses how satisfied a patient is, using a 5-point rating scale from very poor to very good, with 14 items. The items assessed include physical health, mood, work, household activities, social relationships, family relationships, leisure time activities, ability to function in daily life, sexual drive/interest/performance, economic status, living/housing situation, ability to get around physically without feeling dizzy or unsteady or falling, vision in terms of ability to do work or hobbies, and overall sense of well-being that are summed to provide a raw total score ranging from 14 to 70. There are an additional 2 stand-alone items (1 for medication satisfaction and the other for overall life satisfaction). The total raw score is converted to a percent score.

6.2.5 WHO-5 Well-Being Index (Part A Only)

The WHO-5 is a patient-reported outcome measure developed by the World Health Organization. This self-reported questionnaire consists of 5 questions regarding subjective quality of life based on positive mood, vitality, and general interest, each rated on a 6-point Likert scale from 0 (at no time) to 5 (all the time). The sum of scores represents the raw scores with 0 representing the worst possible quality of life and 25 representing the best possible quality of life. A score below 13 represents poor well-being. To calculate the percentage score, the raw score is multiplied by 4, with 100% representing the best possible quality of life. A 10% difference over time indicates a meaningful change. The WHO-5 has been found to have adequate validity as an outcome measure in clinical trials ([Topp, 2015](#)).

6.2.6 NEO-FFI (Part A Only)

The NEO-FFI is a 60-item self-report scale ([Costa, 1992](#)). Each item is rated on a 5-point scale. Twelve items assess each of five dimensions of personality: neuroticism (N), extraversion (E), conscientiousness (C), openness (O), and agreeableness (A).

6.3 Safety and Tolerability Assessments

All patients who receive study drug will be evaluated for safety. Safety assessments will include incidence of AEs, suicidality assessment by the C-SSRS, mania assessment by the YMRS, movement disorder assessment by the AIMS, BARS and SAS, clinical laboratory evaluations, ECG evaluations, vital sign measurements, and physical examination and neurological findings.

6.3.1 Adverse Events

The investigator is responsible for reporting all AEs that are observed or reported during the study, regardless of their relationship to study drug or their clinical significance.

6.3.1.1 Definition of Adverse Event

An AE is any untoward medical occurrence in a study patient administered a study drug, whether or not considered drug related. This can be any unfavorable and unintended sign (such as an abnormal laboratory finding), symptom, or disease temporally associated with the use of a study drug, without any judgment of causality.

The AE may be:

- A new illness;
- A worsening sign or symptom of the condition under treatment, or of a concomitant illness;
- An effect of the study medication, including comparator; or
- A combination of 2 or more of these factors.

No causal relationship with the study medication or with the clinical study itself is implied by the use of the term AE.

Surgical procedures themselves are not AEs; they are therapeutic measures for conditions that require surgery. The condition for which the surgery is required may be an AE. Planned surgical measures, if permitted by the clinical study protocol and the conditions leading to those measures are not AEs.

All AEs fall into the categories of “nonserious” or “serious (Sections 6.3.1.2 and 6.3.1.3).

6.3.1.2 Definition of Serious Adverse Event

An SAE is defined as any untoward medical occurrence that at any dose:

- Results in death;
- Is life threatening;
- Requires hospitalization or prolongation in existing hospitalization;
- Results in persistent or significant disability or incapacity; or
- Is a congenital anomaly or birth defect.

The term “life threatening” refers to an event in which the patient is at risk of death at the time of the event; it does not refer to an event, which hypothetically might have caused death if it were more severe.

Medical and scientific judgment should be exercised in deciding whether an AE is serious. Some important medical events that may not result in death, be life threatening, or require hospitalization may be considered SAEs when they may jeopardize the patient such that medical or surgical intervention is needed to prevent 1 of the outcomes previously listed. Examples of such medical events include intensive emergency treatment for an allergic reaction, blood dyscrasias or convulsions that do not result in inpatient hospitalization, and the development of drug dependency or drug abuse.

If either the sponsor or principal investigator believes that any event is serious, the event must be considered and evaluated by the sponsor for possible expedited reporting.

Clarification of the difference between "serious" and "severe":

The term “severe” is often used to describe the intensity (severity) of a specific event (as in mild, moderate, or severe myocardial infarction); the event itself, however, may be of relatively minor medical significance (such as a severe headache). This is not the same as “serious,” which is based on patient/event outcome or action criteria usually associated with events that pose a threat to a patient’s life or functioning. Seriousness (not severity) serves as a guide for defining regulatory reporting obligations.

6.3.1.3 Nonserious Adverse Event

A nonserious AE is any AE not meeting the SAE criteria.

6.3.1.4 Definition of Relationship to Study Drug

By definition, any AE that starts before the first dose of study drug administration is considered to be “unrelated.”

The investigator will assess the causality/relationship between the study drug and the AE (Table 6–3). One of the following categories should be selected based on medical judgment, considering the following definitions and all contributing factors.

Table 6-3 **Causality Categories**

| Category | Definition |
|------------------------|--|
| Definitely related | A clinical event, including laboratory test abnormality, occurs in a plausible time relationship to treatment administration, and which concurrent disease or other drugs or chemicals cannot explain. The response to withdrawal of the treatment (dechallenge ¹) should be clinically plausible. The event must be definitive pharmacologically or phenomenologically, using a satisfactory rechallenge ² procedure if necessary. |
| Probably related | A clinical event, including laboratory test abnormality, with a reasonable time sequence to administration of the treatment, unlikely to be attributed to concurrent disease or other drugs or chemicals, and which follows a clinically reasonable response on withdrawal (dechallenge). Rechallenge information is not required to fulfill this definition. |
| Possibly related | A clinical event, including laboratory test abnormality, with a reasonable time sequence to administration of the treatment, but which could also be explained by concurrent disease or other drugs or chemicals. Information on treatment withdrawal may be lacking or unclear. |
| Unlikely to be related | A clinical event, including laboratory test abnormality, with a temporal relationship to treatment administration which makes a causal relationship improbable, and in which other drugs, chemicals or underlying disease provide plausible explanations. |
| Unrelated | A clinical event, including laboratory test abnormality, with little or no temporal relationship with treatment administration. May have negative dechallenge and rechallenge information. Typically, explained by extraneous factors (e.g., concomitant disease, environmental factors, or other drugs or chemicals). |

¹ Dechallenge is when a drug suspected of causing an adverse event (AE) is discontinued. If the symptoms of the AE disappear partially or completely, within a reasonable time from drug discontinuation, this is termed a positive dechallenge. If the symptoms continue despite withdrawal of the drug, this is termed a negative dechallenge. Note that there are exceptions when an AE does not disappear upon discontinuation of the drug, yet drug-relatedness clearly exists (e.g., bone marrow suppression, fixed drug eruptions, tardive dyskinesia).

² Rechallenge is when a drug suspected of causing an AE in a specific patient in the past is readministered to that patient. If the AE recurs upon exposure, this is termed a positive rechallenge. If the AE does not recur, this is termed a negative rechallenge.

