3.1.1 Part A Study Periods (up to 10 Weeks, Including Screening/Baseline)

Part A of the study consists of the following periods: screening period, on-treatment period, and safety follow-up period. Patients who rollover directly into Part B will not have a unique safety follow-up visit after the 6-week treatment.

Screening Period (2 Weeks)

Potential patients will be evaluated during a screening period lasting up to 2 weeks, unless confirmed by the medical monitor that a longer screening phase, lasting no longer than 28 days, is appropriate to ensure washout of excluded medications with long half-lives (e.g., fluoxetine), under the supervision of the investigator before baseline.

After obtaining written informed consent, diagnostic interviews and physical examinations will be conducted, vital signs and ECGs will be assessed, and blood samples for laboratory assessments will be collected. Patients considered potentially eligible for participation will be required to discontinue their current antidepressant treatment and/or other psychotropic drugs.

[REDACTED]
[REDACTED]

At baseline (Visit 2), patients who continue to meet all eligibility criteria will be randomly assigned to 1 of the 3 treatment arms for a 6-week, double-blind treatment period. Patients will be randomly assigned to 1 of the following groups: 40-mg ITI-007, 60-mg ITI-007, or matching placebo.

On-Treatment Period (6 Weeks)

Patients will take their first dose of study medication the evening of their baseline randomization visit. A single dose will be taken each day in the evening for the duration of the on-treatment period.

Following randomization, patients will attend the clinic at Weeks 1, 2, 3, 4, 5, and 6.

The on-study treatment period will be a total of 6 weeks.

Safety Follow-up Period (2 Weeks)

For those patients not continuing on to Part B, a return to the clinic for a safety follow-up visit will occur at Week 8, approximately 2 weeks following the last dose of study medication. If possible, patients who discontinue treatment prematurely will be seen for an early termination visit (within 1 week of the last dose of study drug when possible) and will be asked to return to the clinic for a safety follow-up visit 2 weeks following withdrawal.

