5.2 Treatments Administered

In Part A, patients will be assigned to receive either ITI-007 (40- or 60-mg doses) or placebo. Study center personnel will receive a treatment card number from the IVRS/IWRS for each patient at each clinic visit, to ensure that the correct investigational product is dispensed.

Patients will self-administer all doses orally, once daily, at home, in the evening for the duration of the on-treatment period. Treatment will be administered between 8:00 PM and 10:30 PM, at approximately the same time each day whenever possible. Treatments will be provided in dose cards containing 2 strips of over-encapsulated tablets (Section 5.4.1). Patients will be instructed to take 2 capsules (1 capsule from each strip) per dose.

In Part B, all patients will receive ITI-007 (60 mg). Patients will self-administer all doses orally, once daily, at home, in the evening for up to approximately 6 months (175 days) at approximately the same time each day whenever possible. Patients will be instructed to take 1 tablet per dose. (Section 5.3.2).

In Part B, a one-time dose reduction will be allowed for patients who (in the opinion of the investigator and as confirmed by the Medical Monitor) are not tolerating the 60 mg dosage. If the patient is not able to tolerate the 40 mg dose, they must be withdrawn from the study and undergo evaluations required in the early termination visit.

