6.3.1.7 Documenting, Reporting, and Eliciting Adverse Events

All AEs reported or observed during the study will be collected and recorded on the AE page of the eCRF for each patient from the date the ICF was signed until the end of their participation in the study, i.e., the patient has discontinued or completed the study.

Adverse events may be volunteered spontaneously by the patient, or discovered by the study staff during physical examinations or by asking an open, non-leading question such as, “How have you been feeling since you were last asked?” All AEs and any required remedial action will be recorded. The nature of the AE, date (and time, if known) of the AE onset, date (and time, if known) of the AE outcome to date, severity, and action taken for the AE will be documented together with the investigator’s assessment of the seriousness of the AE and causal relationship to study drug and/or study procedure.

All AEs should be recorded individually in the study patient’s own words (verbatim) unless, in the opinion of the investigator, the AEs constitute components of a recognized condition, disease or syndrome. In the latter case, the condition, disease or syndrome should be named rather than each individual symptom. The AEs will subsequently be coded using the latest version of Medical Dictionary for Regulatory Activities (MedDRA).

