7.5.8 Safety Analyses (Parts A and B)

All safety parameters will be summarized using the Safety Analysis Set.

Medical history, prior medications, concomitant medications, and compliance/exposure will be summarized by treatment group using descriptive statistics. Safety data such as reported and observed AEs, TEAEs, SAEs, clinical laboratory results, vital signs, physical examinations and neurological findings, ECGs, and the different rating scales (YMRS, C-SSRS, AIMS, BARS, and SAS) will be summarized by visit (Part A and Part B) and treatment group (Part A). Parameters planned to be collected more than once at pre-specified timepoints will be analyzed as an average of the measures for the relevant time point, including screening and baseline.

[figure not shown]
Observed and reported AE terms will be coded using the latest version of MedDRA. TEAEs will be defined as any AEs, regardless of the relationship to study drug, that occur or worsen in intensity after the first dose of study drug and within 14 days after the last dose of study drug. Study-drug-related TEAEs will be defined as any AEs that are considered by the investigator to be either possibly, probably, or definitely related to study drug. If relationship to study drug is missing, the TEAE will be considered as treatment-related. TEAEs, and SAEs will be listed summarized by SOC, PT, relationship to study drug, intensity (Part A and Part B) and treatment group (Part A). Patients who discontinue study or study drug due to an AE will be listed and summarized by SOC and PT (Parts A and B) and by treatment group (Part A).

Laboratory assessments, including hematology and chemistry, vital signs, and ECGs, will be listed and summarized by visit and time point (Parts A and B and by treatment group (Part A). Summaries will include actual and change from baseline values, incidence of abnormal values according to normal range criteria, shifts from baseline to each visit and

time point according to markedly abnormal criteria, and listings of patients meeting markedly abnormal criteria.

The observed and change from baseline in YMRS, AIMS, BARS, SAS and C-SSRS scores will be summarized by visits (Part A and B) and by treatment group (Part A).

Additional details for analyses on safety parameters will be provided in the statistical analysis plan.

A series of approximately 10 horizontal black bars of varying lengths, indicating redacted text.

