## **7. GENERAL CONSIDERATIONS**

Relative Study Day will be calculated from the date of Day 1, which is the day of first treatment with double-blind study medication in Part A, and will be used to show the start and/or stop days of treatment, study procedures and assessments, prior, concomitant, and post-treatment medications, and adverse events.

[figure not shown]
- If the date of the treatment, procedure, or event is on or after Day 1 date then:

Relative Study Day = (date of variable of interest – Day 1 date) + 1.

- If the date of the treatment, procedure, or event is prior to the Day 1 date then:

Relative Study Day = (date of variable of interest – Day 1 date).

In the situation where the date is partial or missing, Relative Study Day, and any corresponding event durations will appear missing in the listings.

Analyses presented by visit or study day will be based on the scheduled visits as planned in the protocol. Visit windows for unscheduled visits or early discontinuation visits are defined in **Table A**, which provides the mapping of relative day ranges to the scheduled target days and the study periods for Part A. If more than one assessment is available in the same ‘Range of Relative Study Days’ (window), the assessment closest to the Scheduled Target Day will be selected and assigned to the Scheduled Target Day. If two or more assessments are available in the same window and are equidistant from the Scheduled Target Day, the latest assessment will be selected (if before study Part B start). 

Listings will include scheduled, unscheduled, retest and early discontinuation data.

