**Table A: Part A - Mapping of Relative Day Ranges to Schedule Target Day**

Study Phase	Study Period	Range of Relative Study Days	Scheduled Target Day	Scheduled StudyWeek
Pre-Treatment	Screening	1-14* days before Day 1 date	Day -14	-2
Pre-Treatment	Baseline	Day 1 date (definition of baseline varies by assessment – see descriptions below)	Day 1	0
Study Treatment	On-Treatment	2 to 11 days relative to Day 1 date	Day 8	1
Study Treatment		12 to 18 days relative to Day 1 date	Day 15	2
Study Treatment		19 to 25 days relative to Day 1 date	Day 22	3
Study Treatment		26 to 32 days relative to Day 1 date	Day 29	4
Study Treatment		33 to 39 days relative to Day 1 date	Day 36	5
Study Treatment		≥40 days relative to Day 1 date and after the last dose of treatment and before the start of the Safety Follow-up Period (one day after actual Day 43 visit) or Part B study.	Day 43	6
Post-treatment**	Safety Follow-up	> 43 days relative to Day 1 date for treatment completers (42 day on-treatment) and after Day 43 post-treatment assessments.	Day 57	8

\*\* Only for subjects not enrolling over into Part B study phase upon completing treatment in Part A.

First treatment with study medication and baseline assessments are scheduled for Visit 2 on Relative Study Day 1. For analysis purposes, baseline is defined as the last non-missing pre-treatment measurement and endpoint defined as the last Part A On-treatment measurement.

Assessments will be considered baseline if the assessment date is before the date of the first treatment of the 6-week On Treatment Period or if the assessment was done on Study Day 1 and, according to the Study Schedule of Events, was supposed to be performed on Day 1, prior to treatment. Bracket assessments originally scheduled for Day -1 that are rescheduled for Day 1 and are confirmed as taken prior to first dose will be considered baseline.

Unless otherwise specified, the following calculations will be used for change from baseline and percent change from baseline of quantitative measurements:

Change from baseline will be calculated as:

- Value at Visit X – Baseline Value

Percent change from baseline will be calculated as:

- $$\frac{\text{Value at Visit X} - \text{Baseline Value}}{\text{Baseline Value}} \times 100$$

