### **16.1. ADVERSE EVENTS**

Adverse Events (AEs) will be coded using MedDRA central coding dictionary currently in effect at the time of interim analysis or final Part A database lock.

Treatment emergent adverse events (TEAEs) are defined as AEs that started or worsened in severity on or after the date of the first dose of study medication and on or before the date of last dose of study medication in Part A plus one day.

All AEs with an onset date after the last dose of study medication plus one day, but before the start of Part B will be listed in the AE data listing and labelled as 'Follow-up Adverse Event'.

See [Appendix 2](#) for handling of partial or completely missing dates for AEs. In the case where it is not possible to define an AE as treatment emergent or not, the AE will be classified as the worst case, i.e., treatment emergent.

An overall summary of the number of subjects within each of the categories described in the [sub-sections 16.1.1](#) and [16.1.2](#) below will be provided as specified in the TLF shells.

Listings will include all adverse events, TEAEs and Non-TEAEs.

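### The SAP counts every adverse event dated Day 1 as treatment-emergent, although the first dose is taken that evening and the protocol counts only events that occur or worsen after it

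*Protocol*

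**What the plan says.** **Timing of the first dose.** Protocol 3.1.1: "Patients will take their first dose of study medication the evening of their baseline randomization visit". Protocol 5.2 has patients dose themselves at home and gives the hours: "Treatment will be administered between 8:00 PM and 10:30 PM". SAP section 7 defines "Day 1, which is the day of first treatment with double-blind study medication in Part A", and the text under SAP Table A adds: "First treatment with study medication and baseline assessments are scheduled for Visit 2 on Relative Study Day 1". The baseline clinic visit and the first dose therefore share one calendar date, with the visit first.

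**Protocol definitions.** Section 7.5.8 counts as treatment-emergent those events that "occur or worsen in intensity after the first dose of study drug", whatever their relationship to study drug. Section 6.3.1.4 adds that "any AE that starts before the first dose of study drug administration is considered to be" unrelated. Section 6.3.1.7 collects events from the date of consent and asks for more than the date: "The nature of the AE, date (and time, if known) of the AE onset".

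**SAP rule.** Section 16.1 takes "AEs that started or worsened in severity on or after the date of the first dose of study medication". The Appendix 2 algorithm matches it: a known start date equal to the study medication start date gives a TEAE. Neither refers to onset time or to a pre-dose flag. Section 16.1 also has a worst-case default, but only for events that cannot be classified. Section 16.1.1 regards a TEAE with a missing relationship as related.

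**The concern.** The protocol's boundary is the dose; the SAP's boundary is midnight before the dose. Between them lies nearly all of the waking Day 1, including the baseline visit and its blood draws, in patients who have just stopped other psychotropic drugs. Events in those hours are plausible, and they are recorded because collection starts at consent.

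An event whose recorded onset precedes the dose can be classified, so the worst-case default does not explain its inclusion. Elsewhere the SAP does separate these hours. Under Table A, Day 1 assessments scheduled before treatment are baseline. Sections 16.3 and 16.4 treat the pre-dose ECG and the Visit 2 vital signs as baseline. Section 13 relies on an eCRF entry for whether a medication began before the first dose. A finding at the Day 1 visit could thus be baseline in the ECG table and treatment-emergent in the AE table.

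At stake are the TEAE counts, the table of preferred terms reaching 5% in any arm, and the relative risks and chi-square p-values of SAP 16.1.1. For events with a blank relationship field, the related-TEAE summary is affected too.

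**Working it through.** The plan gives no figure for this point, so there is none to reproduce. The check applies each rule to one event and then gauges the size under stated assumptions.

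**1. One test event.** Onset recorded at 10:00 on Day 1; first dose at 20:00 on Day 1; no later worsening.

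| Rule | Comparison | Result |
|---|---|---|
| Protocol 7.5.8 | 10:00 is not after 20:00 | not a TEAE |
| Protocol 6.3.1.4 | 10:00 is before 20:00 | unrelated |
| SAP 16.1 and Appendix 2 | start date = first-dose date | TEAE |
| SAP 16.1.1, relationship blank | TEAE with missing relationship | related |

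Protocol 7.5.8 also treats a missing relationship as related, but only for TEAEs, and its own definition has already removed this event. The conflict with 6.3.1.4 in the last row therefore comes from the SAP's date rule.

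**2. How much of Day 1 is before the dose.** With dosing from 20:00 to 22:30: 20/24 = 83% to 22.5/24 = 94% of the calendar day. If the last dose is on Day 42 (assumption), the SAP's window, which adds one day, is 43 days. The pre-dose share of that window is 20/(43 × 24) = 1.9% to 22.5/(43 × 24) = 2.2%.

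**3. Patients affected.** Assume that 0.5% to 2% of patients have an event starting on Day 1 before the dose. Then 549 × 0.005 = 2.7 and 549 × 0.02 = 11.0 patients in the trial, or 183 × 0.005 = 0.9 and 183 × 0.02 = 3.7 per arm.

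**4. Effect on the relative risk of any TEAE.** Let a and b be the true post-dose risks, and q the pre-dose risk, equal in both arms and independent of later events. The observed ratio is [1 − (1 − a)(1 − q)] / [1 − (1 − b)(1 − q)]. For illustrative risks of 50% v 40% (true ratio 1.25):
- q = 0.5%: 0.5025/0.403 = 1.247
- q = 2%: 0.51/0.412 = 1.238

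**5. Effect on a single preferred term.** Suppose that events of a term accrue evenly over the window at the placebo rate. The added risk is then about 0.02 × the placebo risk:
- 4% v 1% (ratio 4.0): 4.02/1.02 = 3.94
- 10% v 5% (ratio 2.0): 10.1/5.1 = 1.98

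Clustering around the visit procedures would give more. As an upper bound, if all of q fell on the 10% v 5% term, the step 4 formula gives 0.1045/0.05475 = 1.91 at q = 0.5% and 0.118/0.069 = 1.71 at q = 2%.

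**6. Single patients.** With 10/183 v 5/183 (ratio 2.00), one extra patient in both arms gives 11/6 = 1.83, in placebo only 10/6 = 1.67, and in the active arm only 11/5 = 2.20. At the 5% listing threshold, one patient moves a term from 9/183 = 4.9% to 10/183 = 5.5%.

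**The case against.** **The SAP may refine the protocol.** Protocol section 7 lets the SAP change analysis methods without an amendment, and 7.5.8 leaves safety details to it. That is so, but section 7 also requires such changes to be documented. The visible SAP text does not present the date rule as a change. Parts of the SAP are redacted, so a note or an eCRF flag may exist; the visible AE rule uses neither.

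**Counting by date is the cautious choice.** It errs toward including events. This stands where timing is unknown. It is weaker where a pre-dose onset is documented, because background events added to both arms tend to mask a difference.

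**A time rule could lose real drug reactions.** This is the strongest objection, and it limits the remedy. Onset time is recorded only if known. SAP section 14 takes only the date of first dose from the dosing form, and no dose time is visible. Under protocol 6.3.1.5, several intensity changes within a day lead to one maximum for that day. An event that begins at noon and worsens after the evening dose may therefore be a single record with a noon onset. Protocol 5.5.2 also expects some doses at the wrong time of day. A patient who dosed early and reacted before 8:00 PM would be wrongly removed if that hour stood in for the dose time.

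**Unrelated events belong in TEAE tables anyway.** This is correct. A reader might infer from 6.3.1.4 that an unrelated event must be kept out. The documents do not say so: 7.5.8 defines TEAEs regardless of relationship, and SAP 16.1.1 has an unrelated category. The conflict is with the timing in 7.5.8; 6.3.1.4 matters only through the blank-relationship rule.

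**Conclusion.** The inconsistency is real and worth correcting. SAP 16.1 and Appendix 2 classify as treatment-emergent an event that the records place before any drug, contrary to protocol 7.5.8. If its relationship is blank, the SAP also calls it related, contrary to 6.3.1.4.

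The effect is probably small: a few patients, expected to be balanced across arms because the events precede treatment, slightly higher TEAE counts, and relative risks diluted on average. The range of 3 to 11 patients rests on an assumed 0.5% to 2%; the documents give no rate.

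Two stronger readings should be resisted. A reader might infer that every relative risk and chi-square test is pulled toward no difference. With so few events most preferred terms would gain none, and a single patient in one arm can move a ratio away from 1 (step 6). A reader might also put a 0.5% pre-dose risk on one rare term and find a ratio falling from 4.0 to (4 + 0.5)/(1 + 0.5) = 3.0. That needs essentially all of the roughly 2.7 affected patients to share one term, which nothing in the documents suggests.

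**What to change.** Amend SAP 16.1 and the known-start-date rows of Appendix 2. An event dated on the first-dose date is not treatment-emergent only if both conditions hold:

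1. Its onset is documented as pre-dose: the recorded onset time is before the recorded first-dose time, or before study drug was dispensed at Visit 2, or an eCRF flag marks it as pre-dose.
2. There is no record of worsening on or after that date.

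If the timing or any same-day worsening is unclear, keep the event as a TEAE, in line with the existing worst-case default. Do not use 8:00 PM as a proxy for the dose time. Excluded events remain in the listings as non-TEAEs, which SAP 16.1 already provides for. Once they are no longer TEAEs, the blank-relationship rule does not reach them.

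The cost is one added rule and slightly more derivation work, using onset times already collected when known. The visible documents do not show whether a clock time is kept for the first dose or for dispensing; if neither is kept and there is no flag, few events will qualify. Some pre-dose events without a recorded time will also stay in the TEAE tables.
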